Acute Effect of Melon Manis Terengganu Peel
Powder on Glycemic Response, Satiety, and Food
Intake in Adults at Risk for Type 2 Diabetes

NCT05298111

25 March 2022

Study Protocol

Open-label, randomised, placebo-controlled, crossover study with two intervention arms. The study was conducted in 30 participants and the primary objective is to show an improved glycemic response after Melon Manis Terengganu (MMT) peel powder consumption in people at risk of type 2 diabetes. Besides, the acute effect of MMT peel powder on perceived satiety and energy intake were explored.

Pre-test protocol

Participants were required to obtain adequate sleep (7 to 9 hr) on nights before test days (Hirshkowitz et al., 2015). They were instructed by the researchers to maintain their usual daily food intake and consume a dinner of similar composition and quantity at a similar time before their study visit besides avoiding caffeine consumption such as caffeinated beverages, meals or medications as well as alcohol consumption. This is to minimize within-respondent variability (Al-Mana & Robertson, 2018) as well as ensure similar feelings of satiety and glycemic response on study visits (Kay, 2016). Additionally, participants were required to avoid moderate or strenuous activity (as indicated by the IPAQ-SF) before the test days as this would deplete their glycogen content derived from the liver and muscle. Glycogen can be stored for up to 12 to 48 hr, after which the body switches to oxidative fats and ketones metabolism (Lean, 2015).

To ensure that these habits had not been modified during the study, the participants were instructed to record 24-hr dietary recalls (food logs) and physical activity diaries (IPAQ-SF) as well as take photos of any food and drinks they consumed which were reviewed by the researcher on the test days to ensure accuracy and completeness. Any unclear aspect was clarified on the spot. A copy of the food log was kept by the participants for them to refer back to each study visit to preserve meal accuracy, especially dinner meals consumed before each visit.

They were required to fast for 10 to 12 hr preceding their testing time and hence they were instructed to eat their dinner no later than 10 pm. They were only allowed to consume plain water once their testing period began. The pre-test protocols were no longer in effect once participants finished their testing for the day, and they were free to resume their normal activities and food habits.

Data collection

Participants attended the lab at 8 am with light clothing and were asked a series of questions to measure fasting, nutrition, physical activity and sleep regimen adherence. They were also required to hand in the completed questionnaire which consisted of dietary and physical activity information which were distributed to them before data collection. Then, height, weight, waist circumference, % body fat and blood pressure measurement were taken followed by a perceived satiety measurement and fasting capillary blood sample (baseline) withdrawal using the finger pricking method.

After that, the participants were randomized to consume one of the two types of test products namely A: control (glucose) and B: Formulation 3 (60% sweetener) dissolved in 180 mL plain water together with the standardized breakfast in treatment sequences (AB, BA). Each respondent consumed the meals in a separate place and avoided using electronic gadgets while eating to reduce distractions. They were instructed to consume the meals at a comfortable pace within 15 min. Participants were asked to remain rested in the same place during the testing period and allowed to read, use their phone or laptop and use the toilet after meals consumption. They have also refrained from excessive physical activity until the end of test visit.

At the first bite, a timer was started and postprandial blood samples as well as perceived satiety measurement were then taken at 30, 60, 90 and 120 min thereafter. Blood collection techniques adhered exactly as they were written in the standard operating procedure (SOP). After the 120 min assessments, participants were allowed to leave the testing site and instructed to record the food consumed for the rest of the day. The food record was aimed to explore the changes in food intake following each test food relative to usual food intake (baseline data) (Burton-Freeman et al., 2017). Also, they were given a new food log form and physical activity diary to fill in one day before the next study visit. Figure 3.4 displayed the study flow chart.

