Acute Effect of Melon Manis Terengganu Peel Powder on Glycemic Response, Satiety, and Food Intake in Adults at Risk for Type 2 Diabetes

NCT05298111

25 March 2022

Statistical Analysis Plan (SAP)

Data Checking and Normality Test

Data entry errors and respondent's errors may occur during data entry and answering the questionnaire. Data were checked after they were entered into the SPSS. Data checking was crucial to ensure the accuracy of all the entered data, identify any missing data and any outliers during the data entry. Mistyping responses or entering data was an example of data entry errors in contrast to respondent's errors that happened during answering the questionnaire, for example the participants did not complete the questions or provide an unreadable or illogical response.

Before descriptive statistical analysis was performed, the frequency distribution (histogram) and boxplot were used for checking normality visually. Normally distributed population generated a bell-shaped curve appearance of the histogram with symmetrical about the mean indicates data. Besides, the Shapiro-Wilk test was done for the assessment of normality tests and the data considered to be normal if $p > 0.05$. Hence, according to the findings, the data checkinwas g revealed that all the variables have completed 30 valid frequencies for socio-demographic, anthropometry, biochemical, blood pressure, dietary intake, perceived satiety and physical activity information. Those outputs implied that no missing data value was reported.

Statistical Analysis

The data were analysed by using IBM SPSS system version 21.0 and Nutritionist ProTM software (Version 7.0.0, Axxya Systems).

Descriptive Statistic

A descriptive statistic was used to present all outcomes on socio-demographic information, anthropometric measurement, blood glucose levels, blood pressure measurement, dietary intake, perceived satiety and physical activity. Continuous data were described as mean \pm standard deviation if normally distributed or median (interquartile range) if not normally distributed meanwhile for categorical variables, the data were reported as the number of frequency and percentage. The 2 hr area under the curve (AUC) of blood glucose levels (incremental area above the baseline value) and perceived satiety (hunger, fullness, desire to

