eat, prospective food consumption and thirstiness) were calculated using the trapezoidal approximation (Winham et al., 2017). The maximum concentration (Cmax) of blood glucose levels were taken to be the highest concentration within the respective time interval (Stewart & Zimmer, 2017).

Nutritionist Pro was a dietary analysis software used for macronutrient and micronutrient analysis. This software consists of several food databases including the USDA Food Database, Canadian Food Database, Mexico Food Database and the Malaysian Food Composition Tables along with other hundreds of international food items. In this software, if the food item consumed by the participants was not available, the researchers can readily substitute it with other identical food items available in the databases. Besides, the standard recipe was created for food products that could not be found in any of the previously mentioned sources. The dietary intake of the participants for habitual, pre-test and test day were inserted in the software, and subsequently, the interested macronutrients (energy, carbohydrate, protein, fat, and dietary fibre) or micronutrients (calcium, magnesium, zinc, iron, selenium, Vitamin A, E, K, and C) were conveyed to SPSS for further analysis.

Bivariate and General Linear Model Analysis

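### The only contrast is Formulation 3 against a glucose control, so calling the comparator a placebo and crediting any effect to the peel powder needs a match between the drinks that the documents do not state

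*Protocol*

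**What the plan says.** **Products.** The Protocol, under Data collection, gives the two test products as "A: control (glucose) and B: Formulation 3 (60% sweetener) dissolved in 180 mL plain water together with the standardized breakfast". They are taken in the sequences AB and BA, so A versus B is the only comparison.

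**Label.** The opening Study Protocol paragraph describes an "Open-label, randomised, placebo-controlled, crossover study with two intervention arms". The SAP, under Bivariate and General Linear Model Analysis, also names the two conditions as placebo and intervention.

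**Attribution.** The same opening paragraph says "the primary objective is to show an improved glycemic response after Melon Manis Terengganu (MMT) peel powder consumption", and adds that "the acute effect of MMT peel powder on perceived satiety and energy intake were explored". The title carried by both documents reads "Acute Effect of Melon Manis Terengganu Peel Powder on Glycemic Response, Satiety, and Food Intake".

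**Outcome.** The SAP, under Descriptive Statistic, summarises "blood glucose levels (incremental area above the baseline value" over two hours, together with the maximum concentration (Cmax). Baseline is a fasting capillary sample taken before the drink and breakfast.

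**The concern.** A placebo comparison isolates an ingredient when the comparator is the same preparation without it. Here the comparator is identified as glucose and the test product as a formulation with 60% sweetener. Neither description says what the two share.

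This matters more than usual because the comparator is the substance being measured. Sugar taken in the drink comes after the baseline sample, so it can contribute to the area above baseline and to the peak. If A delivers more glucose-raising carbohydrate than the non-peel part of B, then B could show a lower response even with an inert peel. If it delivers less, a real peel effect could be hidden.

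The primary conclusion is at stake: whether the trial may report an effect of peel powder, or only an effect of a particular formulation relative to a glucose drink.

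**Working it through.** No arithmetic applies. The documents give no amount of glucose in A, no identity or amount of the sweetener in B, no meaning for the 60%, no peel content, and no carbohydrate or energy figure for either drink. The check is on what the contrast estimates.

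**1. The contrast.** With two products in sequences AB and BA, the iAUC and Cmax comparisons and the time-course model all rest on B versus A.

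**2. What it contains.** Written additively for simplicity:

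mean(B) − mean(A) = P + N

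P is the effect of the peel. N is the effect of any difference between the drinks in everything other than the peel.

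- If the non-peel ingredients are the same, N = 0 and the contrast equals P.
- If the peel is inert, P = 0 and the contrast equals N.
- Otherwise the contrast is the sum. One equation with two unknowns cannot separate them.

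Taking a lower iAUC as the improvement (an assumption, since the documents do not define it), a negative N would flatter the peel and a positive N would mask it.

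**3. Whether the plan fixes N = 0.**

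| Feature | What it handles | Does it set N = 0? |
|---|---|---|
| Crossover | Stable differences between participants | No |
| Standardized breakfast | Differences in the breakfast | No |
| Covariates (age, ethnicity, gender, BMI; baseline also discussed) | Participant characteristics | No |
| 30 participants | Precision | No |
| Third condition, such as the formulation without peel | Would isolate the peel | None described |
| Statement that the drinks match | Would justify N = 0 | None found |

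**4. Whether the documents show N ≠ 0.** They do not. The sweetener is unidentified and could be glucose in the same amount as in A. The label alone settles nothing.

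**5. Exploratory aims.** The same decomposition applies to satiety and energy intake, since drinks that differ in sugar or energy could affect both. The Protocol frames the food record by product: "The food record was aimed to explore the changes in food intake following each test food relative to usual food intake". That is already the formulation-level wording; the stated aim goes further and names the peel.

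**6. A further gap.** No sentence says outright that Formulation 3 contains the peel powder. This is inferred from the title and objective. Attribution to the peel depends on that content as well as on matching.

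**The case against.** The strongest reply is that this is a gap in reporting and not an error. If B's sweetener is glucose in the same amount as in A, the contrast isolates the peel and the present wording is right. The name Formulation 3 and the reference to a Figure 3.4 suggest that the pages come from a longer document, where composition may be described. A is also openly identified as glucose in the sentence that defines the products, so a careful reader is not misled about what was given.

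Much of this stands. A reader might infer that the drinks are mismatched, that the 60% label points to a sweetener with little glucose, or that the result is biased in favour of the formulation. The documents support none of these: they give no sweetener type and no amounts, so neither a mismatch nor its direction can be shown. A reader might also see a contradiction in the SAP's neutral reference to two products beside its use of placebo. There is none, because it is a collective term that the Protocol also uses.

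The point about inference remains. The objective attributes the effect to one ingredient, and the contrast supports that only under a condition found nowhere in the plan. The missing figure is described as a study flow chart, so it is unlikely to supply the composition. Disclosing that A is glucose does not establish that A is B without the peel.

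**Conclusion.** The concern holds as a limit on what the trial may conclude. On the documents as written, a difference in iAUC or Cmax supports a statement about the MMT formulation compared with a glucose control. It supports a statement about the peel powder only if the non-peel ingredients of the two drinks are the same in type and amount.

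The size and direction of any bias cannot be computed and it may be zero; no figure in the documents converts into an effect on iAUC or Cmax. This conclusion rests on the text of both documents and on the inference that Formulation 3 contains the peel. It does not rest on any assumed difference between the drinks. Confidence is medium, because records not included here may show that the drinks match. It should be fixed, since the headline attribution depends on it.

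**What to change.** 1. Call the comparator a glucose control in the Protocol and the SAP.
2. State the glycemic objective, the exploratory satiety and energy-intake aims, and their conclusions as the effect of the MMT formulation compared with the glucose control.
3. Keep the placebo label and the attribution to the peel only if the formulation records show that the non-peel ingredients of A and B are the same in type and amount. Report those ingredients together with the peel content of B. The comparison should be of non-peel ingredients and not of total carbohydrate or energy: if the peel itself supplies either, drinks identical apart from the peel would differ in their totals.
4. Change the report title only if matching cannot be shown.

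The cost is rewording, plus one composition table if the records hold the figures. No new data collection is needed. The downside is a possibly narrower claim. The records may also be incomplete: the SAP describes the dietary software for participants' intake ("The dietary intake of the participants for habitual, pre-test and test day were inserted in the software") and does not say that the test products were analysed. In that case the wording in steps 1 and 2 applies.

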Acute Effect of Melon Manis Terengganu Peel Powder on Glycemic Response, Satiety, and Food Intake in Adults at Risk for Type 2 Diabetes

NCT05298111

25 March 2022

Statistical Analysis Plan (SAP)

Data Checking and Normality Test

Data entry errors and respondent's errors may occur during data entry and answering the questionnaire. Data were checked after they were entered into the SPSS. Data checking was crucial to ensure the accuracy of all the entered data, identify any missing data and any outliers during the data entry. Mistyping responses or entering data was an example of data entry errors in contrast to respondent's errors that happened during answering the questionnaire, for example the participants did not complete the questions or provide an unreadable or illogical response.

Before descriptive statistical analysis was performed, the frequency distribution (histogram) and boxplot were used for checking normality visually. Normally distributed population generated a bell-shaped curve appearance of the histogram with symmetrical about the mean indicates data. Besides, the Shapiro-Wilk test was done for the assessment of normality tests and the data considered to be normal if $p > 0.05$. Hence, according to the findings, the data checkinwas g revealed that all the variables have completed 30 valid frequencies for socio-demographic, anthropometry, biochemical, blood pressure, dietary intake, perceived satiety and physical activity information. Those outputs implied that no missing data value was reported.

Statistical Analysis

The data were analysed by using IBM SPSS system version 21.0 and Nutritionist ProTM software (Version 7.0.0, Axxya Systems).

Descriptive Statistic

A descriptive statistic was used to present all outcomes on socio-demographic information, anthropometric measurement, blood glucose levels, blood pressure measurement, dietary intake, perceived satiety and physical activity. Continuous data were described as mean \pm standard deviation if normally distributed or median (interquartile range) if not normally distributed meanwhile for categorical variables, the data were reported as the number of frequency and percentage. The 2 hr area under the curve (AUC) of blood glucose levels (incremental area above the baseline value) and perceived satiety (hunger, fullness, desire to

eat, prospective food consumption and thirstiness) were calculated using the trapezoidal approximation (Winham et al., 2017). The maximum concentration (Cmax) of blood glucose levels were taken to be the highest concentration within the respective time interval (Stewart & Zimmer, 2017).

Nutritionist Pro was a dietary analysis software used for macronutrient and micronutrient analysis. This software consists of several food databases including the USDA Food Database, Canadian Food Database, Mexico Food Database and the Malaysian Food Composition Tables along with other hundreds of international food items. In this software, if the food item consumed by the participants was not available, the researchers can readily substitute it with other identical food items available in the databases. Besides, the standard recipe was created for food products that could not be found in any of the previously mentioned sources. The dietary intake of the participants for habitual, pre-test and test day were inserted in the software, and subsequently, the interested macronutrients (energy, carbohydrate, protein, fat, and dietary fibre) or micronutrients (calcium, magnesium, zinc, iron, selenium, Vitamin A, E, K, and C) were conveyed to SPSS for further analysis.

Bivariate and General Linear Model Analysis

A paired t-test (normally distributed) or Wilcoxon matched pair signed-rank sum test (non-normally distributed) was used to compare the difference of two data between groups (placebo and intervention) on anthropometric measurements, blood glucose levels (iAUC and CMax), blood pressure, dietary intake, physical activity and perceived satiety (AUC). Two-way repeated measures ANCOVA was used to compare the postprandial blood glucose levels between two test products over different time points, controlling for treatment and time to test for treatment by time interaction after adjustment for covariates (age, ethnicity, gender and BMI) (Tongyu & Chong-Do, 2021; J. Wang et al., 2021). Rather than subtracting from baseline data alone, including baseline data as a covariate will improve the analyses' performance. Furthermore, due to random deviations at baseline, the use of baseline subtraction can result in artefactual effects (whether these differences are statistically significant or not) (Blundell et al., 2010). The perceived satiety was analysed using the Friedman non-parametric test. The analysis was considered significant at a p -value ≤ 0.05 . Any significant data was further tested using Wilcoxon matched pair signed-rank sum test.

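### The protocol's intake aim is energy, but the SAP's product comparison appears to take in 14 dietary variables at p ≤ 0.05 each, with no lead variable

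*SAP*

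**What the plan says.** The protocol's opening section (Study Protocol) makes glycemic response the primary objective and adds that "the acute effect of MMT peel powder on perceived satiety and energy intake were explored". Energy is the only intake variable named there. The protocol's Data collection section is wider: "The food record was aimed to explore the changes in food intake following each test food relative to usual food intake (baseline data").

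In the SAP, the Descriptive Statistic section lists five macronutrient variables and nine micronutrients for export: "energy, carbohydrate, protein, fat, and dietary fibre) or micronutrients (calcium, magnesium, zinc, iron, selenium, Vitamin A, E, K, and C) were conveyed to SPSS". It also says that "The dietary intake of the participants for habitual, pre-test and test day were inserted in the software".

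The Bivariate and General Linear Model Analysis section applies a paired t-test, or a Wilcoxon signed-rank test if the data are not normal, between placebo and intervention to a list that includes "blood glucose levels (iAUC and CMax), blood pressure, dietary intake, physical activity and perceived satiety (AUC"). The list gives a summary measure for glucose and for satiety but none for dietary intake. The criterion follows: "The analysis was considered significant at a p -value" of 0.05 or less. Neither document gives a lead intake variable, an order of testing or a multiplicity rule.

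**The concern.** The protocol's aim sentence points to one intake variable. The SAP carries 14 forward, and the only between-product analysis it gives for dietary data is the paired test at 0.05. The natural reading is 14 tests of equal standing.

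An isolated p-value below 0.05 for zinc or vitamin K, say, would then meet the plan's own definition of significance. It could be reported as an effect of the product on food intake beside the energy result, and nothing in the SAP would tell the reader to weigh it differently. The SAP also does not say which of the habitual, pre-test and test-day records enter the comparison, so even the test of energy is not fully defined.

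**Working it through.** The documents give no family-wise error rate and no power calculation, so there is no stated figure to reproduce.

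**Inputs from the documents**
- Dietary variables: 5 + 9 = 14 (SAP, Descriptive Statistic).
- Threshold: 0.05 per test, with no adjustment (SAP, Bivariate and General Linear Model Analysis).
- Participants: 30, each receiving both products (Study Protocol and Data collection).

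**Assumption**
- The correlation between nutrients in the paired differences is not given. It is taken as equal for all pairs and varied from 0 to 0.7.

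**Step 1: expected number of false positives.** If the product affects none of the variables, this is 14 × 0.05 = 0.70, whatever the correlation. For the 13 variables other than energy it is 13 × 0.05 = 0.65.

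**Step 2: chance of at least one, under independence.** The formula is 1 − 0.95^k.
- k = 14: 1 − 0.95^14 = 0.512
- k = 13 (energy set aside): 1 − 0.95^13 = 0.487
- k = 9 (micronutrients only): 1 − 0.95^9 = 0.370

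**Step 3: chance of at least one, with correlation.** For each correlation, 20,000 null trials were simulated with 30 normally distributed paired differences per variable and two-sided paired t-tests at 0.05.

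| Equal correlation | All 14 | 13 without energy |
|---|---|---|
| 0 | 0.51 | 0.48 |
| 0.2 | 0.47 | 0.45 |
| 0.3 | 0.44 | 0.42 |
| 0.5 | 0.36 | 0.34 |
| 0.7 | 0.25 | 0.24 |

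The simulated values at zero correlation agree with the formula within simulation error.

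**Step 4: which row is realistic.** Energy is largely the sum of carbohydrate, protein and fat, and all 14 variables come from the same food records. The zero-correlation row therefore cannot apply and serves as a ceiling for the equal, non-negative correlations considered here. Even at 0.7 the rate is about five times the nominal 5% (0.25 / 0.05 = 5).

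**Step 5: after the change proposed below.** With one intake test at 0.05, the chance of a false significant intake result is 0.05.

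**The case against.** Four points on the other side deserve weight.

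1. *The 14 tests are inferred.* The nutrient list stands under descriptive statistics and is sent on only for further analysis. The later section names dietary intake as a block. That same list includes anthropometry and blood pressure, which are measured before the product is given, so part of it may serve to check comparability between visits. This stands as a caution. Fourteen tests is the natural reading of the two sections together, but the SAP does not say so outright.

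2. *The aim is not purely energy.* The study title and the Data collection section both speak of food intake, and macronutrients could fall within that. This stands too. However, a wider aim makes a named lead variable more necessary, and no stated aim mentions a micronutrient.

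3. *Intake is exploratory.* The protocol says so, and the primary conclusion is untouched. Whether exploratory nutrient tests need a formal adjustment such as Holm is a matter of preference. But the SAP applies one significance rule to everything and does not carry the exploratory label over to nutrients.

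4. *Stronger readings go too far.* A reader might infer that a chance nutrient finding is more likely than not. That rests on 51.2% under independence, which cannot hold, and it counts energy itself as one of the chance findings; the other 13 give 48.7%. A reader might also count pre-test-day intake and reach 28 tests, with 1 − 0.95^28 = 0.762. But that intake precedes the product and is recorded to confirm stable habits, so a difference there could not be presented as a product effect.

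**Conclusion.** The concern holds as a matter of reporting and of how clearly the plan is specified. On the natural reading of the SAP, 14 dietary variables are compared between products at p ≤ 0.05 each, with none in the lead. If there is no true effect on any of them, the chance of at least one false significant result is about 44% at correlation 0.3, 36% at 0.5 and 25% at 0.7, with 51% as the ceiling under independence.

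These figures assume that all 14 variables are tested once, on one record day, with equal correlation between them. The correlations are assumed, since the documents give none. The finding does not bear on the primary glycemic conclusion.

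**What to change.** In the SAP's Bivariate and General Linear Model Analysis section:

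- Name test-day energy intake, B versus A, as the only intake variable tested at 0.05, as the protocol's aim sentence already implies.
- Report the other 13 nutrients as exploratory paired differences with 95% confidence intervals and no significance statement. Use the mean difference where the data are normal and the Hodges–Lehmann median difference where they are not, in line with the SAP's existing split between the t-test and the Wilcoxon test.
- Use pre-test-day intake only to describe comparability between visits.
- State that energy was chosen because the protocol names it and not because of the data. This is needed because the Data Checking and Normality Test section reports that data checking was already done, so a change now cannot simply be presented as prespecified.

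The cost is a few sentences of SAP wording and no new data. The downside is that no significance claim can be made for an individual nutrient, but none is named in the protocol's aim sentence.

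### iAUC and Cmax are tested by a paired comparison with no period term and no fasting-glucose covariate; the test is valid over random allocation, but it can lose power

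*SAP*

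**What the plan says.** - The Protocol's opening section states that "the primary objective is to show an improved glycemic response" in people at risk of type 2 diabetes, in a crossover study of 30 participants.
- Protocol, Data collection: each product is taken "together with the standardized breakfast in treatment sequences (AB, BA"), after a "fasting capillary blood sample (baseline) withdrawal using the finger pricking method". The text gives neither the method of randomisation nor the number per sequence.
- SAP, Descriptive Statistic: the glucose AUC is the "blood glucose levels (incremental area above the baseline value"). For the peak, "The maximum concentration (Cmax) of blood glucose levels were taken to be the highest concentration within the respective time interval".
- SAP, Bivariate and General Linear Model Analysis: "A paired t-test (normally distributed) or Wilcoxon matched pair signed-rank sum test (non-normally distributed) was used to compare" the two products on iAUC and Cmax, among other variables. A separate repeated-measures ANCOVA of the glucose time course adjusts for age, ethnicity, gender and BMI. The sentence saying that "including baseline data as a covariate will improve" the analysis comes after that ANCOVA.
- No analysis in the SAP has a period or sequence term.

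**The concern.** iAUC and Cmax are the only summary measures of the glycemic response, and their test leaves out two things that the trial already has.

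**Period.** If the second visit differs systematically from the first, that difference enters the within-person contrast with one sign in AB and the opposite sign in BA. Left in the error term, it widens the standard error. If the sequences are unequal in size, part of it also moves the estimate, and a reader without the split cannot see by how much.

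**Fasting glucose.** Subtracting it, as iAUC does, is fully efficient only if post-meal glucose moves one-for-one with the fasting value. Ignoring it, as Cmax does, is fully efficient only if the peak does not depend on it. The true slope may lie between these and may differ between the two outcomes.

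With 30 people, a real product effect could be missed that the same data would have shown. I do not claim that the SAP contradicts itself, because its sentences on baseline may be meant for the ANCOVA alone.

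**Working it through.** **Inputs.** From the documents: n = 30, two sequences, significance at p ≤ 0.05 (two-sided assumed), no missing data. The documents give no effect size, SD, power target, period effect or split, so there is no planned figure to reproduce. Everything below is in SDs of the within-person difference (B minus A) and rests on assumed values.

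**Model.** Difference = τ + π in sequence AB and τ − π in sequence BA, plus error with SD 1. Here π is the period effect.

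**Target effect.** With period fitted at 15/15, the standard error is √[¼(1/15 + 1/15)] = 0.183 on 28 df. Power of 80% needs τ = 0.530 (noncentral t). The paired test with no period effect then also has 80%.

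**Period-fitted power at other splits.**
- 18/12: standard error √[¼(1/18 + 1/12)] = 0.186, power 78%.
- 20/10: standard error √[¼(1/20 + 1/10)] = 0.194, power 75%.
- Averaged over simple randomisation: 79%. None of these depends on π.

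**Paired test (simulated).**

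| π | Type I error, simple randomisation | Power, simple randomisation | Power, 15/15 | Type I error, 15/15 | Type I error, 20/10 |
|---|---|---|---|---|---|
| 0.25 | 5% | 78% | 78% | 4% | 6–7% |
| 0.5 | 5% | 71% | 73% | 3% | 10% |
| 1.0 | 5% | 50% | 50% | 1% | 17% |

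At 15/15 the loss arises because the variance grows by about 1 + π²: 1.06, 1.25 and 2.00.

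**Shift given an unequal split.** The paired estimate moves by π(nAB − nBA)/30. At π = 0.5 this is 0.5 × 6/30 = 0.10 SD for 18/12 and 0.5 × 10/30 = 0.17 SD for 20/10. At 18/12 the type I error stays near 5%, but power at π = 0.5 is 53% if the shift opposes the effect and 87% if it favours it, against 78% fitted. Under simple randomisation, a split of 18/12 or worse has probability 0.36, and 20/10 or worse 0.10.

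**Fasting glucose.** For readings at 0, 30, 60, 90 and 120 minutes, all above baseline, the incremental area has weights −105, 30, 30, 30 and 15. If post-meal glucose has slope b on fasting glucose, fasting variation with SD s contributes (1 − b) × 105 × s to iAUC and b × s to Cmax. I assume s = 0.3–0.5 mmol/L within person, and residual SDs of 60 mmol·min/L (iAUC) and 0.8 mmol/L (Cmax). If all are taken per visit, differencing doubles every variance and the ratios do not change.

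- iAUC variance ratio = 1 + [(1 − b) × 105 × s]²/60². Example: b = 0.5, s = 0.5 gives 1 + 26.25²/3600 = 1.19.
- Cmax variance ratio = 1 + (b × s)²/0.8². Example: b = 0.5, s = 0.5 gives 1 + 0.0625/0.64 = 1.10.

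| Slope b (each outcome has its own) | Excess variance, iAUC | Excess variance, Cmax |
|---|---|---|
| 0.2 | 18–49% | 1–2% |
| 0.5 | 7–19% | 4–10% |
| 0.8 | 1–3% | 9–25% |
| 1.0 | 0% | not computed |

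**Net effect of fitting both terms.** If neither matters, power is about 78% at 15/15, 77% at 18/12, 73–74% at 20/10 and 77% averaged, against 80% for the paired test. With baseline irrelevant, the two-term model overtakes the paired test at π of about 0.23 (15/15) or 0.29 (averaged). With no period effect, it breaks even when the fasting difference and the outcome difference correlate at about 0.2 at 15/15, which is an excess variance of 0.04/0.96 = 4%. Averaged over simple randomisation, break-even lies between 0.2 and 0.3 (4–10%). At 15/15 and no period effect, correlations of 0.3 and 0.5 give 82% and 89%.

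**The case against.** The planned test is valid over the randomisation and conservative at 15/15, so this is a matter of efficiency. No period effect or fasting slope can be read from the documents, so even the sign of the net gain is unproven. The Protocol standardises sleep, evening meal, fasting, caffeine, alcohol, activity and arrival time, in its words "This is to minimize within-respondent variability", which may leave little period effect. At π = 0.25 the two-term model gains nothing on average. The smallest baseline losses in the table (1–3%) are less than the fix costs, and the 49% is the extreme corner of the assumed range. The SAP names no primary endpoint, and the time-course ANCOVA also addresses glycemic response. A split as uneven as 20/10 is unlikely.

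Most of this stands, and it limits the point to lost power of uncertain size. It does not remove it. The ANCOVA's covariates do not reach iAUC or Cmax, and it has no period term either. Standardised visits make a period effect less likely without excluding it. The possible cost of adjustment is two or three points of power on average (six or seven at 20/10), while the possible gain over the assumed range is much larger. Without the number per sequence, a reader cannot judge whether any shift matters.

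**Conclusion.** The concern holds. The tests of iAUC and Cmax use neither the randomised order nor, beyond subtraction in iAUC, the fasting sample. They keep the 5% error rate over random allocation. The loss of power runs from nil, when period effects are small and fasting glucose adds little, to about 30 points at a period effect of 1.0 SD. Given an unequal split, a period effect also shifts the estimate in proportion to the imbalance. These sizes rest on assumed period effects, SDs and slopes, so confidence is medium. The change should be made, but its absence does not invalidate the trial.

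**What to change.** For iAUC and for Cmax, regress the within-person difference (B minus A) on sequence, coded +1/−1, and on the B-minus-A difference in fasting glucose. Leave the fasting difference uncentred, so that the intercept is the product effect at zero fasting difference. Report the estimate with its 95% CI and the number of participants per sequence.

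If the residuals are clearly non-normal, by a criterion written down beforehand, compare the period 1 minus period 2 differences between sequences with a rank-sum test. This handles period but not baseline. In simulated normal data its power is 78% at 15/15, 76% at 18/12 and 72–73% at 20/10, whatever the period effect.

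If the SAP is amended before the outcome analysis, make this model primary and the paired test a sensitivity analysis. Otherwise keep the paired test as planned and report the adjusted model beside it, labelled as added after data collection. The SAP already describes the data as checked and analysed, so the second route may be the only one left.

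The cost is a few lines of SPSS syntax, two degrees of freedom and the small power loss shown above if neither term matters. No new data are needed. A period term does not deal with carryover.
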